### 7.1. Treatments Administered

Study Treatment Name:	GSK2798745	Matching Placebo	Challenge Agent: GMP grade lipopolysaccharide from Escherichia coli (E. Coli Group 0113:H10:K Negative) for the segmental LPS challenge
Dosage formulation:	White to slightly coloured, round biconvex tablet. Product: AP, Tab-A	White to slightly coloured, round biconvex tablet. Product code: CET, Tab-A..	LPS is available from stock lyophilized in a 1 microgram vial, formulated in 1% lactose and 0.1% PEG6000. Clear solution.
Unit dose strength(s)/Dosage level(s):	Unit dose strength 2.4 mg. Dosage Levels: 4.8 mg and 2.4 mg	Not applicable	4 ng/kg
Route of Administration	Oral	Oral	Direct application to the lung segment, via bronchoscopy
Dosing instructions:	Two tablets to be taken on the morning of Day 1, then one tablet to be taken 12 hours later.	Two tablets to be taken on the morning of Day 1, then one tablet to be taken 12 hours later.	One single instillation of 10 mL by bronchoscopy 2 hours after dosing with GSK2798745 or placebo on Day 1.

Study Treatment Name:	GSK2798745	Matching Placebo	Challenge Agent: GMP grade lipopolysaccharide from Escherichia coli (E. Coli Group 0113:H10:K Negative) for the segmental LPS challenge
Packaging and Labeling	GSK2798745 tablets will be provided in high-density polyethylene (HDPE) bottles with child-resistant closures that include induction-seal liners. Each bottle will be labelled as required per country requirement.	Placebo tablets will be provided in high-density polyethylene (HDPE) bottles with child-resistant closures that include induction-seal liners. Each bottle will be labelled as required per country requirement.	-
Manufacturer	GSK	GSK	List Laboratories, Inc.

Sterile saline (0.9%) for control challenge will be sourced by the clinical site.

### 7.1.1. Dose Modification

No dose modifications are permitted without submission of a substantial amendment to the protocol.

## 7.2. Challenge Agents

Bacterial endotoxin is a component of the cell wall of Gram-negative bacteria present in a variety of occupational and general environmental settings.

The dose of LPS used in this study is 4 ng/kg, which is 100 times lower than doses used in inhalation models of endotoxin-induced lung inflammation. This dose was chosen based on the data published by O'Grady et al [O'Grady, 2001]. In this study, lavage after 24-h in subjects challenged with 4 ng/kg of endotoxin revealed a localised inflammatory response that was neutrophil-predominant. The site performing this study has experience with this model. The LPS challenge agent to be used for the procedure is Good Manufacturing Practice (GMP)-grade product and will be sourced from List Laboratories, Inc. A certificate of analysis will be provided for each batch of the LPS challenge agent to ensure its quality and safety.

Reconstitution will be done under the responsibility and supervision of the investigator or qualified site staff who performs the bronchoscopy and administers the reconstituted LPS in individual dilution to the subject. The reconstitution will be done on the day of bronchoscopy immediately before the procedure (within 1 hour). If more than one subject per day will be investigated, the first process of reconstitution and administration of LPS has to be completed before a second process is started.

The reconstitution process is described as an example for the nominal dose of 10,000 EU of endotoxin per vial. Each vial of LPS contains a lyophilized solid containing 10,000 EU of endotoxin. Upon reconstitution with 5 mL of sterile saline 0.9%, the vial will contain 2,000 EU/mL = 2 EU/ $\mu$ L. Forty (40)  $\mu$ L/kg body weight will be withdrawn from the vial and transferred into a sterile endotoxin-free 30 mL-sample vial (Acila AG, Weiterstadt, Germany). Sterile saline 0.9% will be added to give a final volume of 20 mL. Ten (10) mL of this solution contains the application dose of 40 EU (4 ng)/kg, and will be filled into a 10 mL-syringe. This individual dilution will be administered to the participant by segmental pulmonary application during the bronchoscopy. The remaining 10 mL will be stored frozen (-20°C) as a retention sample.

The negative control will be performed with 10 mL of sterile saline 0.9% only. The reconstitution process will be adapted to the actual endotoxin content as determined in the Certificate of Analysis. The Investigator Site File will contain the current instructions for reconstitution in order to ensure the application dose of 40 EU/kg.

### **7.3. Method of Treatment Assignment**

All participants will be centrally randomized using an Interactive Web Response System (IWRS). Before the study is initiated, the log in information and instructions for the IWRS will be provided to each site. Participants will be registered using the IWRS, and assigned a unique number (randomisation number). The randomisation number encodes the participant's treatment (GSK2798745 or placebo), according to the randomization schedule generated prior to the study by the Statistics Department at GSK. Each participant will be dispensed blinded study treatment, labelled with his/her unique randomisation number.

### **7.4. Blinding**

This will be double blind study. All study staff involved in clinical assessments (which includes the investigator, sub-investigators, other site staff) and the participant will be blinded to the treatment allocated to individual participants and to post challenge total protein in BAL sample results. Selected sponsor study team members (and delegates if programming activities are outsourced) will be unblinded to perform the interim analysis. This may include the medical monitor, study statistician, study programmer (and delegates) and study pharmacokineticist. Access to unblinded data will be kept to the minimum set of individuals required to implement any interim analyses, but may include GSK management/review committees if alterations to the study conduct are required. Details of who were unblinded to what data and when will be included in the clinical study report. The IWRS will be programmed with blind-breaking instructions. In case of an emergency, the investigator has the sole responsibility for determining if unblinding of

a participant's treatment assignment is warranted. Participant safety must always be the first consideration in making such a determination. If the investigator decides that unblinding is warranted, the investigator should make every effort to contact GSK prior to unblinding a participant's treatment assignment unless this could delay emergency treatment of the participant. If a participant's treatment assignment is unblinded GSK must be notified within 24 hours after breaking the blind. The date and reason that the blind was broken must be recorded in the source documentation and CRF, as applicable.

A participant whose treatment assignment is inadvertently unblinded (either to investigative staff or the participant themselves) will be permitted to remain in the study, although the accidental unblinding will be recorded as a protocol deviation and hence the participant will be subject to review as to their inclusion in analyses.

GSK's Global Clinical Safety and Pharmacovigilance (GCSP) staff may unblind the treatment assignment for any participant with an SAE. If the SAE requires that an expedited regulatory report be sent to one or more regulatory agencies, a copy of the report, identifying the participant's treatment assignment, may be sent to investigators in accordance with local regulations and/or GSK policy.

## **7.5. Preparation/Handling/Storage/Accountability**

1. The Investigator or designee must confirm appropriate temperature conditions have been maintained during transit for all study treatment received and any discrepancies are reported and resolved before use of the study treatment.
2. Only participants enrolled in the study may receive study treatment and only authorised site staff may supply or administer study treatment. All study treatments must be stored in a secure, environmentally controlled, and monitored (manual or automated) area in accordance with the labeled storage conditions with access limited to the investigator and authorised site staff.
3. The investigator, institution, or the head of the medical institution (where applicable) is responsible for study treatment accountability, reconciliation, and record maintenance (ie, receipt, reconciliation, and final disposition records).
4. Further guidance and information for the final disposition of unused study treatment are provided in the SRM.
5. Under normal conditions of handling and administration, study treatment is not expected to pose significant safety risks to site staff.
6. A Material Safety Data Sheet (MSDS)/equivalent document describing occupational hazards and recommended handling precautions either will be provided to the investigator, where this is required by local laws, or is available upon request from GSK.

## **7.6. Treatment Compliance**

- When the individual dose for a participant is prepared from a bulk supply, the preparation of the dose will be confirmed by a second member of the study site staff.

- When participants are dosed at the site, they will receive study treatment directly from the investigator or designee, under medical supervision. The date and time of each dose administered in the clinic will be recorded in the source documents. The dose of study treatment and study participant identification will be confirmed at the time of dosing by a member of the study site staff other than the person administering the study treatment. Study site personnel will examine each participant's mouth to ensure that the study treatment was ingested.
- GSK2798745 and the placebo will be orally administered to participants at the site.

## **7.7. Concomitant Therapy**

### **7.7.1. Permitted Medications**

Paracetamol, at doses of  $\leq 2$  grams/day, is permitted for use any time during the study. Rescue medication, such as salbutamol, is also permitted after bronchoscopy or spirometry procedure, if required, and other medication, such as midazolam, may be taken during bronchoscopies to aid the procedure. Other concomitant medication may be considered on a case-by-case basis by the investigator in consultation with the Medical Monitor if required.

### **7.7.2. Prohibited Medications**

Except for the permitted medications noted above (Section [7.7.1](#)), participants must abstain from taking prescription or non-prescription drugs (including vitamins and dietary or herbal supplements) within 7 days (or 14 days if the drug is a potential enzyme inducer) or 5 half-lives (whichever is longer) before the start of study treatment until completion of the follow-up visit, unless, in the opinion of the investigator and sponsor, the medication will not interfere with the study.

## **7.8. Treatment after the End of the Study**

Participants will not receive any additional treatment from GSK after completion of the study because only healthy volunteers are eligible for study participation.

## **8. DISCONTINUATION CRITERIA**

### **8.1. Individual Stopping Criteria**

#### **8.1.1. Liver Chemistry Stopping Criteria**

**Increased monitoring criteria** have been designed to assure participant safety and evaluate liver event etiology (in alignment with the FDA premarketing clinical liver safety guidance). These protocol guidelines are in alignment with FDA premarketing clinical liver safety guidance:

<http://www.fda.gov/downloads/Drugs/GuidanceComplianceRegulatoryInformation/Guidances/UCM174090.pdf>.

Increased monitoring will be performed for a participant if liver chemistry stopping criteria are met.

Liver Safety Required Actions and Follow up Assessments Section can be found in [Appendix 6](#)

#### **8.1.2. QTc Stopping Criteria**

The QTc should be based on single or averaged QTc values of triplicate electrocardiograms obtained over a brief (e.g., 5-10 minute) recording period.

A participant who meets either bulleted criterion below will be withdrawn from study:

- QTcF >500 msec
- Change from baseline of QTc >60 msec

#### **8.1.3. Symptoms of Cardiac Ischaemia and Cardiac Troponin Stopping/Increased monitoring Criteria**

##### **8.1.3.1. Asymptomatic Participant**

Cardiac troponin (cTn) will be measured before and at the end of the study. If any cTn assessment is >ULN or >2 times the participant's baseline value (Day -1), the participant should be contacted immediately to assess for symptoms of cardiac ischemia.

##### **8.1.3.2. Symptomatic Participant**

If a participant experiences symptoms of cardiac ischaemia (e.g. chest pain, increased shortness of breath, and diaphoresis), cardiology consultation should be obtained immediately. The participant should be evaluated by a cardiologist and undergo any clinically appropriate testing. The participant should be followed up until symptoms are resolved. If the event occurs after the first dose, but before the second, the participant should not receive the second dose.

#### **8.1.4. Bronchoscopy Stopping Criteria**

A participant will be withdrawn from the study if they experience symptomatic bradycardia or tachycardia requiring treatment as a consequence of bronchoscopy, BAL and LPS instillation. In addition, participants who have the following may also be withdrawn at the discretion of the investigator:

- Oxygen saturation <90% (on oxygen)
- Prolonged somnolence following administration of midazolam
- Significant hypertension/hypotension

#### **8.2. Withdrawal from the Study**

- A participant may withdraw from the study at any time at his/her own request, or may be withdrawn at any time at the discretion of the investigator for safety, behavioural, compliance or administrative reasons.
- If the participant withdraws consent for disclosure of future information, the sponsor may retain and continue to use any data collected before such a withdrawal of consent.
- If a participant withdraws from the study, he/she may request destruction of any samples taken and not tested, and the investigator must document this in the site study records.
- Refer to the SoA (Section 2.3) for data to be collected at the time of withdrawal.

#### **8.3. Study Stopping Criteria**

If there is a serious unexpected adverse event considered at least possibly related to the investigational product administration in one participant; or a severe non-serious AEs considered as, at least, possibly related to the investigational product administration in two participants, the study will be temporarily halted until full review of the events. In participants, significant changes from baseline measurements will be reviewed and participants will be followed until resolved. Participants who have been dosed at the time of the study halt will continue in the study, as planned. Further participants may be dosed only if, after review, the sponsor and investigator consider it safe to do so and only after ethics and regulatory approval of a substantial amendment.

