### **3.3. Benefit/Risk Assessment**

#### **3.3.1. Risk Assessment**

More detailed information about the known and expected benefits and risks and reasonably expected adverse events of GSK2798745 may be found in the Investigator's Brochure.

All potential risks of GSK2798745 are based on pre-clinical data. No risks have been identified in the clinical studies of GSK2798745 conducted before the effective date of this protocol.

Potential Risk of Clinical Significance	Summary of Data/Rationale for Risk	Mitigation Strategy
Investigational Product (IP) [GSK2798745]		
Vascular lesions	
Dogs (4-week study): at 30 mg/kg/day, 2 males had arterial lesions
 
 
• One male: Heart – Coronary artery inflammation; Thymus – Arteriole inflammation with fibroplasia
 
• One male: Epididymides – Artery degeneration/necrosis with inflammation
 
 
Dogs (13-week study): At 10 mg/kg/day, 1 male and 1 female had arterial lesions
 
 
• One male: Epididymides – Arteriole degeneration/necrosis with lymphocytic inflammation
 
• One female: Bladder – Arteriole degeneration/necrosis with lymphocytic inflammation
 
	
Participant Monitoring: The arterial lesions noted in heart, thymus, epididymides, and urinary bladder cannot be monitored directly. There is currently no human translation biomarker or understanding of the underlying mechanism.
 
Participant Exposure: Since these effects cannot be monitored directly in clinical studies, coverage of <math>\geq 30</math> fold will be maintained from the no-effect dose (3 mg/kg/day); exposure will not intentionally exceed the average daily area under concentration-time curve (AUC) of 0.513 hr*<math>\mu</math>g/mL and/or maximum observed plasma concentration (Cmax) of 0.050 <math>\mu</math>g/mL on an individual basis.

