Theoretical risk: Potential suicidal ideation	GSK2798745 is considered to be a CNS-active drug. There has been some concern that some CNS-active drugs may be associated with an increased risk of suicidal thinking or behaviour when given to some patients with certain conditions. GSK considers it important to monitor for such events before or during clinical studies with CNS-active compounds. Participants being treated with GSK2798745 should be assessed at screening for suicidality.	Participant Selection: The risk of such an event would be very low in single-day dose trials in healthy volunteers; however, participants who, in the investigator/designee's judgement, poses a significant suicide risk, will be excluded from the study. A C-SSRS questionnaire will be completed before and after dosing.
Study procedures-related		
Risk of adverse events following delivery of LPS	Previously reported segmental LPS related adverse events include pleuritic pain, pyrexia, head ache, nausea and alveolitis [Hohlfeld, 2008; Holz, 2015]. It is known that LPS and pro-inflammatory mediators can cause gut permeability [Al-Sadi, 2014; Guo, 2013]. We expect the systemic exposure to LPS and systemic inflammatory response to LPS to be minimal following the segmental topical dose of 4ng/kg LPS. As such, we assess the risk to increased gut permeability, and potential increased bioavailability, with this regimen to be low.	Participant Monitoring: Participants will be monitored with safety assessments, including clinical laboratory tests, physical examination, ECGs, vital signs (including temperature), pulse oximetry and spirometry during the study. Experienced site staff will conduct the procedures. Participants will be carefully monitored and managed with standard procedures in the event of complications.
Risks associated with bronchoscopy and BAL sampling:	Procedure related complications include cough, transient fever, chills and myalgias, transient infiltrates, bronchospasm, transient fall of lung function, transient decrease in baseline PaO2 (partial pressure of oxygen in arterial blood).	

Potential Risk of Clinical Significance	Summary of Data/Rationale for Risk	Mitigation Strategy
Risk associated with blood draws	Fainting, mild pain, bruising, irritation or redness.	Experienced site staff will follow standard approaches for managing events related to blood draws.

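### Protocol 8.3 has no automatic study halt for a serious unexpected event attributed only to bronchoscopy, lavage or the saline challenge, and on the more natural reading none for one attributed only to LPS

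*Protocol*

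**What the plan says.** Protocol 8.3 (Amendment 2) is the only place in the two documents with a defined, event-driven safety halt of the whole study. It has two limbs. The first is a serious unexpected adverse event "considered at least possibly related to the investigational product administration in one participant". The second is severe non-serious events in two participants, with the same attribution. Either one halts the study temporarily until the events have been reviewed.

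Two sentences then say what follows. For those already treated: "Participants who have been dosed at the time of the study halt will continue in the study, as planned". For others, dosing may resume only if the sponsor and investigator judge it safe, and "only after ethics and regulatory approval of a substantial amendment".

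The risk table in 3.3.1 heads the drug's risks "Investigational Product (IP) [GSK2798745" and places LPS delivery, bronchoscopy and BAL under a different heading for study procedures. For LPS it states: "Previously reported segmental LPS related adverse events include pleuritic pain, pyrexia, head ache, nausea and alveolitis". For bronchoscopy and BAL: "Procedure related complications include cough, transient fever, chills and myalgias, transient infiltrates, bronchospasm". Section 9.2 times both challenges from the first dose of the investigational medicinal product. In the other direction, the table in 7.1 gives LPS its own column in the study-treatment-name row, beginning "Challenge Agent: GMP grade lipopolysaccharide from".

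**The concern.** Everyone in this study who is challenged, on active drug or placebo, is a healthy volunteer with no expected benefit. Each is planned to have an LPS instillation, a saline instillation and two bronchoscopies (9.1, 9.2), and the protocol itself names harms from these. The only defined halt rule nevertheless asks whether the drug may have caused the event.

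Suppose a volunteer has a serious unexpected reaction during bronchoscopy with an evident procedural cause, or after an instillation where the preparation is suspected. Attribution to GSK2798745 is then the wrong test for whether the next volunteer should be exposed. Section 7.2 allows more than one volunteer in a day, provided the first LPS preparation and administration are finished before the second begins. A decision to pause may therefore be needed quickly, and nothing in 8.3 makes it automatic.

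**Working it through.** The plan states no figure to reproduce here. The check is of wording, followed by a count of planned exposures.

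**Step 1. What the halt rule covers.**

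- Drug: covered by both limbs.
- Bronchoscopy, BAL, saline: procedures or a control instillation, and not investigational product on any reading. Not covered.
- LPS: 3.3.1 separates it from the investigational product, and 9.2 gives it two hours after that product. Section 7 defines study treatment broadly and 7.1 lists LPS as one, but 8.3 speaks of the investigational product, not of study treatment. The more natural reading is that LPS is not covered, but the text is ambiguous.

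**Step 2. Whether another provision fills the gap.**

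| Provision | What it does | Requires a study-level pause? |
|---|---|---|
| Protocol 8.1.4 | Withdraws the individual after certain bronchoscopy, BAL or LPS events | No |
| Protocol 8.2 | Lets the investigator withdraw any participant for safety | No |
| Protocol 9 | Refers immediate concerns to the sponsor, to decide on that participant's study treatment | No |
| Protocol 9.5.1, 9.5.4 | 24-hour SAE reporting; notification of regulators and ethics committees | No |
| Appendix 3, regulatory and ethical considerations | Permits urgent changes to remove an immediate hazard | No, permissive |
| Appendix 3, study and site closure | Lets the sponsor terminate at any time | No, discretionary |
| SAP 3.1 | Recruitment continues during an interim analysis unless safety or tolerability concerns emerge | No defined trigger or review step |

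The protocol does recognise the missing category elsewhere. Section 9.5.1 collects SAEs related to mandated procedures and invasive tests, and Appendix 4 has causality verified against the product or study participation. Section 8.3 does not use that category.

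**Step 3. How many events fall in the gap.** The event must be serious, unexpected, and judged not even possibly related to the drug. That judgement is made by site staff who "will be blinded to the treatment allocated to individual participants", with the challenge at two hours and a median Tmax of 1.5 h (5.4). Many events will therefore be called possibly drug-related and will trigger the existing rule. The remainder are those with a clear procedural or challenge cause. The documents give no rate for them, so no probability is calculated.

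**Step 4. Exposure still planned.** Let k be the participant with the event and N the total challenged. Section 10.3.4 places the interims at about 10 and 20 per arm, with a maximum of 30 per arm, so N = 20, 40 or 60.

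- Remaining LPS instillations = N − k. For k = 10: 20 − 10 = 10; 40 − 10 = 30; 60 − 10 = 50.
- Planned bronchoscopies in those participants = 2(N − k): 20, 60, 100.

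These are planned exposures. Actual numbers could be lower, through withdrawal or a discretionary stop. They could also be higher, since enrolment continues during interims (10.3.4) and non-evaluable participants may be replaced (5.2).

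**The case against.** The strongest case on the other side is that the gap is too small to matter and that judgement would fill it. A blinded assessor, with drug at its peak and a threshold of mere possibility, will seldom exclude the drug. Most of that stands, and it makes the gap narrow. It does not close it: Appendix 4 tells the investigator to weigh alternative causes, so a procedure-only attribution remains open. Appendix 4 also sets a stricter test for a reasonable possibility, but that is a different phrase from the one in 8.3 and nothing equates the two. It should not be used to argue that such attributions will be common.

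The harms listed in 3.3.1 are anticipated, so most would not be unexpected and would trip neither the present limb nor an extended one. That also stands. The list shows that the procedures carry risk, not that the gap will often be reached.

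A reader might infer that challenges must carry on after such an event. The documents do not say so: the provisions in 8.2, Appendix 3 and SAP 3.1 all permit stopping. The site SOPs and the study reference manual, to which 9.1 and 9.2 refer, are not available and may contain a pause procedure.

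A reader might also infer that 8.3 obliges a volunteer dosed less than two hours before a halt to receive LPS, because those dosed continue as planned. Section 8.2 allows that person to be withdrawn for safety. Moreover, the Amendment 2 summary records that sentence, together with the restart condition, as added at the competent authority's request, and neither is in Amendment 1. It is agreed text and not an oversight.

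**Conclusion.** The point holds in a limited form. On its wording, 8.3 has no automatic study-level halt for a serious unexpected event judged related only to bronchoscopy, BAL or the saline challenge. On the more natural reading it has none for an event related only to LPS. In those cases a pause is discretionary.

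The conclusion rests on the protocol and SAP alone. For LPS it also rests on giving 3.3.1 and 9.2 more weight than the layout of the table in 7.1. The 10, 30 or 50 further instillations after an event in participant 10 show what would remain planned. It is tempting to read them as the least that would follow, or as harm caused by the rule, but they are neither. This is a matter of volunteer safety that should be corrected; it does not bear on the primary analysis.

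**What to change.** Extend only the serious-unexpected limb of 8.3. It should cover one such event at least possibly related to the investigational product, the LPS or saline challenge, or bronchoscopy/BAL. No new participant should then be dosed or challenged until the sponsor and investigator have completed their review. Naming LPS also removes the ambiguity. Leave the severe non-serious limb unchanged, so that severe but non-serious procedural reactions do not cause repeated halts.

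Name the reference for expectedness of challenge and procedure events, for example the study-procedures list in 3.3.1. This matters because Appendix 4 treats doubtful hospitalisations as serious and 9.1 foresees overnight observation after bronchoscopy. Without a reference, a precautionary night could stop the study.

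The cost is a few sentences, using the existing review, and an occasional pause after a rare event. If the restart condition is kept for these halts, resuming would need approval of a substantial amendment; 8.3 should say whether it is.

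Any change for participants dosed but not yet challenged when a halt falls is optional. Because it touches wording that the competent authority asked for, it should be raised with the authority as a clarification, noting that 8.2 already permits withdrawal for safety.
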